Several groups reported a correlation between *CYP2D6* variants and reduced tamoxifen efficacy (Table 1). German investigators evaluated the predictive value of genetic variants of *CYP2D6*, *CYP2C19*, and three other cytochrome P450 enzymes for tamoxifen treatment outcome. Tamoxifen-treated patients carrying the *CYP2D6* alleles that are associated with impaired formation of antiestrogenic metabolites including *4, *5, *10, *41, had significantly more recurrences of breast cancer, shorter relapse-free periods and worse event-free survival rates compared with carriers of functional alleles. Interestingly, patients with the *CYP2C19* high enzyme activity promoter variant *17 had a more favorable clinical outcome than carriers of *1, *2, and *3 alleles (11). In a Korean cohort, the authors reported that *CYP2D6* status influenced tamoxifen metabolism in the adjuvant setting, and response to the treatment in the metastatic setting in women with or without variants in the gene (12). Results from 67 Japanese patients revealed similar results (13). Finally, in the Italian chemoprevention study, women who received tamoxifen who were *CYP2D6**4/*4 carriers had a higher likelihood of developing breast cancer (14). At the same time, three large studies have not demonstrated an association (7, 8, 15).

Of note, *CYP2D6* does not appear to be a prognostic marker in breast cancer. In one cohort, samples were obtained from women who did not receive systemic therapy. A significant correlation was not observed between genotypes and tumor size, nodal status, histologic grade, or ER status. In the women who did not receive tamoxifen, there was no association between metabolizer status and outcome ($P = 0.37$) (11).

Table 1. Summary of studies to date correlating CYP2D6 variants with clinical outcome, [modified from (10)]

Author Year	Setting and Study Summary	Patients: Number and Characteristics	CYP2D6 variants	Other Genotypes	Comments ^{&}	Outcomes
Goetz 2005 (4)	Adjuvant. Retrospective review of participants in a prospective study.	256 Post-menopausal. ER-positive.	*4, *6	CYP3A5*3		CYP2D6*4/*4 vs other: RFS HR 1.85, P=0.176. DFS HR 1.86, P=0.089. No association found with CYP3A5*3
Goetz 2007 (5)	Adjuvant. Retrospective Same cohort as Goetz 2005.	190 Post-menopausal. ER-positive.	*4, *6		13 patients on inhibitors	PM vs other: TTR HR 1.91, P=0.034. RFS HR 1.74, P= 0.017.

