_____ 3.1.7.2.1 Chemotherapy or trastuzumab or bevacizumab in the adjuvant setting is allowed but must have been completed at least 4 weeks prior to study registration. Other prior non-hormonal investigational agents in the adjuvant setting must have completed at least 4 weeks prior to study registration and should be discussed with the study PI.

_____ 3.1.7.2.2 Prior aromatase inhibitors (e.g. anastrozole, letrozole, exemestane, aminoglutethamide) are allowed in the adjuvant setting.

The following treatments (3.1.7.2.3 and 3.1.7.2.4) are allowed provided that the patient must have discontinued the agents 6 months prior to study registration:

_____ 3.1.7.2.3 Prior tamoxifen as adjuvant treatment is allowed as long as the patient did not have disease relapse or progression while on adjuvant tamoxifen or within 4 weeks of last dose.

_____ 3.1.7.2.4 Patients who have received other agents that modulate or downregulate the estrogen receptor (e.g. raloxifene, fulvestrant) in the adjuvant setting are eligible if they were on treatment for at least 6 months prior to disease progression in the locally advanced or metastatic setting.

Rev. 8/12

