3.1.7.3 Locally Advanced or Metastatic Setting

_____ 3.1.7.3.1 Patients must not have had more than 2 lines of non-hormonal treatment in the locally advanced or metastatic setting, including trastuzumab (Herceptin), bevacizumab, or other agents; treatment in the locally advanced or metastatic setting must have been completed at least 2 weeks prior to study registration.

_____ 3.1.7.3.2 Prior aromatase inhibitors (e.g. anastrozole, letrozole, exemestane, aminoglutethamide) are allowed in the locally advanced or metastatic setting.

_____ 3.1.7.3.3 Prior tamoxifen is not allowed in the locally advanced or metastatic setting.

_____ 3.1.7.3.4 Patients who have received other agents that modulate or downregulate the estrogen receptor (e.g. raloxifene, fulvestrant) in the locally advanced or metastatic setting are eligible if they were on treatment for at least 6 months and must have discontinued these agents 6 months prior to study registration

_____ 3.1.8 Non-protocol concurrent hormonal therapy is not allowed.

_____ 3.1.9 Concurrent chemotherapy is not allowed.

Rev. 5/11

_____ 3.1.10 Patients, must have adequate hematologic and renal function at the discretion of the treating physician and hepatic function as defined by the following within 4 weeks prior to registration:

_____ 3.1.10.1 Total bilirubin \leq 1.5 x upper limit of normal

Total bilirubin: _____ ULN: _____

Date of Test: _____

Rev. 8/12

_____ 3.1.10.2 SGPT (ALT) \leq 2.5 x upper limit of normal OR \leq 5 x upper limit of normal if liver metastases.

ALT: _____ ULN: _____

Date of Test: _____

Rev. 8/12

_____ 3.1.10.3 SGOT (AST) \leq 2.5 x upper limit of normal OR \leq 5 x upper limit of normal if liver metastases.

AST: _____ ULN: _____

Date of Test: _____

Rev. 5/11

_____ 3.1.11 Patients with a history of central nervous system metastasis are allowed provided they have been treated (surgery, radiation, or radiosurgery) at least 4 weeks prior to initiating study drug and do not require medication(s) to control symptoms. Patients with known leptomeningeal disease are not eligible.

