Rev. 5/11	 3.1.12	Patients may receive concurrent radiation therapy to painful sites of bony disease or areas of impending fracture as long as the radiation therapy is initiated prior to study entry and sites of measurable and non-measurable disease outside the radiation therapy port are available to follow. Patients who have received prior radiation therapy must have recovered from toxicity of the prior radiation therapy.
	 3.1.13	Patients must not take the following medications that are strong to moderate inhibitors of CYP2D6 and may alter tamoxifen metabolism: paroxetine (Paxil), fluoxetine (Prozac), bupropion (Wellbutrin) and quindine (Cardioquin) within 2 weeks of registration.
	 3.1.14	Patients must not suffer from medical or psychiatric conditions that would interfere with protocol compliance, the ability to provide informed consent, or assessment of response or anticipated toxicities.
	 3.1.15	Patients must be disease-free of prior invasive malignancies for \geq 5 years with the exception of curatively-treated basal cell or squamous cell carcinoma of the skin or carcinoma in situ of the cervix.
Rev. 5/11, 8/12	 3.1.16	Patients may not initiate bisphosphonate or denosumab therapy while receiving treatment on this study. Patients who have begun receiving bisphosphonate or denosumab therapy prior to registration may continue at the same intervals used prior to study registration.
	 3.1.17	Patients must be disease-free of prior invasive malignancies for \geq 5 years with the exception of curatively-treated basal cell or squamous cell carcinoma of the skin or carcinoma in situ of the cervix.
Rev. 5/11	 3.1.18	Patients may not initiate bisphosphonate therapy while receiving treatment on this study. Patients who have begun receiving bisphosphonate therapy prior to registration may continue at the same intervals used prior to study registration.

Rev. 5/14 4. Registration Procedures

CTEP Investigator Registration Procedures

Food and Drug Administration (FDA) regulations and National Cancer Institute (NCI) policy require all investigators participating in any NCI-sponsored clinical trial to register and to renew their registration annually.

Registration requires the submission of:

- a completed **Statement of Investigator Form** (FDA Form 1572) with an original signature

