5.4 Supportive Care

All supportive measures consistent with optimal patient care will be given throughout the study.

Patients receiving bisphosphonate therapy prior to beginning this trial may continue at the same intervals used prior to entering the study. Bisphosphonate therapy may not be initiated while being treated on this trial.

Patients must not take the following medications that are strong to moderate inhibitors of CYP2D6 and may alter tamoxifen metabolism: paroxetine (Paxil), fluoxetine (Prozac), bupropion (Wellbutrin), and quindine (Cardioquin) 2 weeks prior to registration or at any time while on-study.

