8.1.12 References

- Legha SS. Tamoxifen in the treatment of breast cancer. Ann Intern Med 1988; 109:219-228.
- Love RR. Tamoxifen therapy in primary breast cancer: Biology, efficacy and side effects. J Clin Oncol 1989; 7:803-815.
- Please see tamoxifen package insert for more information.

9. Statistical Considerations

The primary purpose of this study is to evaluate whether patients with blood samples with CYP2D6 score of 0 (poor metabolizer) have a reduced progression-free survival (PFS) relative to patients with samples with a CYP2D6 score of 1 or 2 (intermediate and extensive metabolizers, respectively). A total of 240 patients will be enrolled in this study. Assuming a monthly accrual of 10 patients, 24 months of accrual is needed. The below calculations assume that 85% (204/240) of the patients enrolled have samples where a CYP2D6 score of 0, 1, or 2 can be assigned.

CYP2D6 SCORING

We will use a scoring system that has been recently modified from Gaedigk et al (18) to include known CYP2D6 variants and inhibitors:

CYP2D6 Allele	Points Assigned/Alele
*1, *1xN, *2, *2xN, *35	1
*9, *10, *17, *41	0.5
*3, *4, *5, *6, *11	0
Medication	Points Adjustment
Paroxetine, Fluoxetine, Bupropion	-2
Sertraline, Duloxetine, Citalopram, Escitalopram, Celecoxib, Diphenhydramine, Chlorpheniramine	-1
Venlafaxine	-0

An overall comparison of patients with scores CYP2D6=0 vs. CYP2D6= 1 or 2 with respect to progression-free survival will be made. It is estimated that approximately 10% will have a score=0, 40% with a score=1 and 50% with a score=2. A hazard ratio (HR) greater than 1.95 or 2 is of interest to influence change in practice. The table below shows the HRs that can be detected with 80% power when all patients have been followed at least 3 months and disease in 180/204 (88%) has progressed. A log-rank test with a 2-sided 5% type I error rate will be used for the comparison.

Hazard Ratios that can be detected with 80% power

Prevalence of patients with CYP2D6 Score=0				
8%		10%		12%
2.09		1.95		1.86

For example, if 10% of the patients have samples with a CYP2D6 score=0, there is 80% power to detect a hazard ratio of 1.95 (comparing score=0 to score=1 or 2).

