Due to the disproportionate expected percentage of poor vs. intermediate and extensive metabolizers, Cox proportional hazards models will be used to estimate the effect of CYP2D6 score with respect to PFS while adjusting for possible confounding factors such as prior AI use and other biomarkers that are being assessed in this study, to assess the

effect of prior AI use and other biomarkers alone with respect to PFS, and to test for interactions between the various baseline factors with respect to PFS.

Due to the low estimated percentage of patients with a CYP2D6 score =0, a stopping rule is incorporated into this design. If the rate of accrual of poor metabolizers is less than 8% or less than 1 patient with a CYP2D6 score=0 per month in the first 18 months that the study is open, the study will be suspended for further evaluation of feasibility.

The distribution of progression-free survival for the patients with a CYP2D6 score=0, 1, and 2 will be estimated using the Kaplan Meier method. Best overall response rate will be summarized as a proportion overall and within patients with a CYP2D6 score=0 vs. 1+2 and within score=0, 1, and 2. Proportion progression-free at 6 months will be summarized overall and within patients with CYP2D6 score=0 vs. 1+2, and within score=0, 1, and 2. Endoxifen levels will be summarized descriptively overall and within responders and non-responders. Comparisons between responders and non-responders with respect to endoxifen levels will be explored using a Wilcoxon rank sum test.

Safety Monitoring

Interim analyses of toxicity are performed twice yearly for all ECOG-ACRIN studies. Reports of these analyses are sent to the ECOG-ACRIN Principal Investigator or Senior Investigator at the participating institutions. Expedited reporting of certain adverse events is required, as described in Section [5.2](#).

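### Cheap improvement, not an error: the PFS test that carries the type I error is unstratified, while prior AI use, a confounder the plan itself names, is adjusted for only in Cox models with no stated decision role

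*Combined protocol and SAP*

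**What the plan says.** Section 9 (Statistical Considerations) makes score 0 against score 1 or 2 on PFS the main purpose of the study. On the test it says: "A log-rank test with a 2-sided 5% type I error rate will be used for the comparison". The table of detectable hazard ratios is built on this comparison, and no stratification factor appears anywhere in the document. On group size: "It is estimated that approximately 10% will have a score=0".

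The same section then plans Cox models that estimate the score effect while "adjusting for possible confounding factors such as prior AI use" and other biomarkers. These models have no type I error rate, no power statement and no stated role in the decision. The plan labels neither analysis primary or secondary. That the log-rank decides is an inference from its being the only PFS analysis with an error rate and a power calculation.

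All patients receive the same tamoxifen regimen (Section 5.1). Section 1.2 describes entry with or without prior AI therapy, and Sections 3.1.7.2.2 and 3.1.7.3.2 allow AI in the adjuvant and the advanced setting.

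**The concern.** The plan identifies a possible confounder and leaves it out of the test that appears to decide the question. Score defines the groups, so neither randomisation nor stratified entry limits imbalance, and about 20 patients make up the smaller group. If prior AI use predicts PFS, an unstratified test loses some power even when AI use is balanced. When AI use is uneven, the p-value shifts in a direction set by the imbalance. If the log-rank and the AI-adjusted Cox result disagreed, the plan does not say which would stand.

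**Working it through.** **1. The plan's own figures.** Inputs from Section 9: 204 evaluable patients, 180 events, 24 months of accrual, at least 3 months of follow-up, two-sided 5%, 80% power. With exponential PFS, uniform accrual and the reference hazard solved to give 180 events, the detectable HR satisfies

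log(HR) / sqrt(1/d1 + 1/d0) = 1.960 + 0.842 = 2.802.

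At 10% prevalence d1 = 19.62 and d0 = 160.38, so sqrt(1/19.62 + 1/160.38) = 0.239 and HR = exp(2.802 × 0.239) = 1.95. At 8% and 12% the same method gives 2.09 and 1.86. All three stated values reproduce, so the power table has no error.

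**2. Set-up for comparing the tests.** Simulation with 204 patients, 20 of them score 0 (10% of 204 = 20.4). Exponential PFS with reference median 6 months (assumed), uniform 24-month accrual, cut-off at the later of the 180th event and month 27. The documents give neither the share with prior AI use nor its effect on PFS. Assumed: 50% prior AI, independent of score; AI HR 1.0, 1.5 or 2.0. The HR of 1.95 is read as the overall (marginal) score effect, which corresponds to 1.99 and 2.06 within AI strata at AI HR 1.5 and 2.0.

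**3. Power averaged over all trials.**

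| AI HR | Unstratified | Stratified | Difference |
|---|---|---|---|
| 1.0 | 80.8% | 80.1% | -0.7 |
| 1.5 | 80.9% | 82.4% | +1.5 |
| 2.0 | 80.1% | 85.5% | +5.4 |

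- The loss at AI HR 1.0 is 0.6-0.8 points across 16, 20 or 24 score-0 patients (the plan's 8, 10 and 12%).
- Over AI prevalence 30-70% the gain is 1.1-1.7 points (AI HR 1.5) or 3.8-5.4 points (AI HR 2.0).
- At AI HR 2.0, a median PFS of 4, 6 or 12 months gives gains of 5.2, 5.5 and 5.4 points (81.0 to 86.2, 79.9 to 85.4, 80.4 to 85.8%).
- If 1.95 is instead the effect within AI strata, power goes from 78.2 to 79.7% (AI HR 1.5) and from 74.1 to 79.5% (AI HR 2.0), similar gains.
- Overall null rejection is 5.3-5.7% for both tests. The excess over 5% is small-sample behaviour that both share.

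**4. Chance imbalance.** With X ~ Bin(20, 0.5) and Y ~ Bin(184, 0.5), the exact probability that X/20 and Y/184 differ by at least 0.10 is 40.5%, about 20% in each direction. For at least 0.20 it is 9.1%.

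**5. Results given the observed gap** (unstratified vs stratified):

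| Score 0 relative to score 1 or 2 | AI HR | Null rejection | Power |
|---|---|---|---|
| At least 10 points more AI | 1.5 | 6.7 vs 5.5% | 87 vs 82% |
| At least 10 points more AI | 2.0 | 8.3 vs 5.7% | 91 vs 86% |
| At least 10 points less AI | 1.5 | 4.8 vs 5.2% | 73 vs 82% |
| At least 10 points less AI | 2.0 | 6.0 vs 5.8% | 67 vs 85% |

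The two directions partly offset each other. In the remaining 59.5% of trials null rejection is about 5.2 vs 5.5% (AI HR 1.5) and 4.6 vs 5.5% (AI HR 2.0), which is why the overall error stays sound.

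**The case against.** The strongest reply is that an unstratified log-rank followed by an adjusted Cox model is an accepted plan. The AI-adjusted score effect will be estimated anyway, so the proposal only changes which result leads. That stands, and it is why this is an improvement and not a defect.

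The size of the gain also rests on an AI prevalence and effect that the documents do not give. That stands too; the ranges show what depends on them. The large contrasts in step 5 must be read in both directions: the unstratified test has more power than the stratified one when score 0 happens to have more AI use, though that excess comes from the imbalance and not from the score.

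A reader might infer that the primary test is biased by confounding, with inflated overall type I error. The documents do not support this, because nothing in them links prior AI use to score:

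- Section 1.2 reports from one cohort: "A significant correlation was not observed between genotypes and tumor size, nodal status, histologic grade, or ER status". It also found no association with outcome in women not given tamoxifen.
- The drugs that subtract 2 points are barred by Section 3.1.13 ("within 2 weeks of registration") and Section 5.4 ("2 weeks prior to registration or at any time while on-study").
- The drugs that subtract 1 point are not on that list, but no connection from them to AI use is shown.

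A reader might also infer that the stated power is overstated. Step 1 shows that it is not.

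**Conclusion.** The point holds as a low-cost improvement that should be made. The only PFS test with a type I error rate omits a covariate that the plan already intends to adjust for. Stratifying protects the result against the imbalance actually observed, which reaches 10 points in about two trials in five by chance alone. Averaged over trials, the effect runs from a loss of under 1 power point (AI not prognostic) to a gain of about 5 points (AI HR 2.0). These figures assume 50% AI prevalence, exponential PFS and independence of score and AI use. Under independence the benefit is power, and an error rate near nominal given the observed gap; there is no invalid overall error rate to repair.

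**What to change.** Make the primary test a log-rank stratified by prior AI use, any or none, as known at registration. Equivalently, name the AI-adjusted Cox test of score 0 against 1 or 2 as primary. Report the unstratified log-rank as a sensitivity analysis.

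Use only this one two-level stratum, given about 20 score-0 patients. Keep the multivariable Cox model for the treatment history it cannot cover: adjuvant versus metastatic AI, adjuvant tamoxifen (Section 3.1.7.2.3: "Prior tamoxifen as adjuvant treatment is allowed"), and earlier non-hormonal lines (Section 3.1.7.3.1: "Patients must not have had more than 2 lines of non-hormonal treatment in the locally advanced or metastatic setting").

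Cost: no new visits, samples or patients, since prior AI use is already a planned covariate. Section 9 should note that its power table was computed for the unstratified test, and the amendment should give the reason for changing the primary test. The downside is under 1 power point if AI use is not prognostic. Any-or-none also pools adjuvant and metastatic AI, so it removes only part of any imbalance in treatment history.

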9.1 Gender and Ethnicity

Based on previous data from E1103, the anticipated accrual in subgroups defined by gender and race is:

Ethnic Category	Gender		
	Females	Males	Total
Hispanic or Latino	13		13
Not Hispanic or Latino	227		227
Ethnic Category: Total of all subjects	240		240
Racial Category			
American Indian or Alaskan Native	0		0
Asian	4		4
Black or African American	44		44
Native Hawaiian or other Pacific Islander			
White	192		192
Racial Category: Total of all subjects	240		240

The accrual targets in individual cells are not large enough for definitive subgroup analyses. Therefore, overall accrual to the study will not be extended to meet individual subgroup accrual targets.

10. Pathology Review

NOTE: ECOG-ACRIN requires that all biological samples submitted be entered and tracked via the online ECOG-ACRIN Sample Tracking System (STS). An STS shipping manifest form must be generated and shipped with the sample submissions. See Section [10.4](#).

10.1 Pathological materials from the primary tumor and metastatic site, when available, should be submitted for banking for future studies.

The clinical investigator and the submitting pathologist have the responsibility for submitting pathology materials for banking. When a patient is registered to receive protocol therapy, the submitting pathologist and clinical research associate should refer to [Appendix II](#) (Pathology Submission Guidelines) which provides the following:

- 10.1.1 Instruction Sheet from ECOG-ACRIN Central Biorepository and Pathology Facility providing details for the Submission of Pathology Materials.
- 10.1.2 Memorandum to the submitting pathologist from [name]., chair, ECOG-ACRIN Laboratory Science and Pathology Committee, providing details for the Submission of Pathology Materials.
- 10.1.3 A list of required materials.

10.2 Materials Required For This Protocol

10.2.1 Forms

- A copy of the surgical pathology report
- Immunologic studies, if available
- Sample Tracking System Shipping Manifest Form (see Section [10.4](#))
 - If STS is unavailable, complete ECOG-ACRIN Generic Specimen Submission Form (#2981). Please identify the clinical status of the submitted material (i.e., pretreatment as opposed to remission and relapse). Please log information into STS once accessible.

In addition to the surgical pathology report, if immunologic studies have been performed at the home institution, it is necessary that these be forwarded as well.

10.2.2 Pathology Sample Submissions

- Original diagnostic paraffin embedded primary tumor block and block from metastatic site (when available).

NOTE: If unable to submit blocks submit fifteen (15) 5-micron sections on uncharged slides or contact the CBPF for alternatives at [name] or [contact].

NOTE: Submit only from patients who have consented to banking.

10.3 Shipping Procedures

Log the samples into the ECOG-ACRIN Sample Tracking System (STS) the day of shipment. If the STS is unavailable, an Generic Specimen Submission Form (#2981) must be submitted with the samples. Once STS is available, retroactively log the shipment into STS, using the actual collection and shipping dates.

